1.2 Study objectives and endpoints

Study objectives and related endpoints are described in [Table 1-1](#) below.

Table 1-1 Objectives and related endpoints

Objectives	Endpoints

Primary Objective
 
 To demonstrate superiority of hydroxychloroquine or hydroxychloroquine plus azithromycin compared to placebo in achieving clinical response by Day 15 	
Endpoints for primary objective
 
The percentage of participants who achieve clinical response by Day 15 defined as:
 
 For participants with a pre-morbid oxygen requirement: 
 Discharge (or ready for discharge as evidenced by normal body temperature and respiratory rate, and stable oxygen saturation on ambient air or \leq 2L supplemental oxygen) OR Survival without need for mechanical ventilation For participants without a pre-morbid oxygen requirement: 
 Discharge (or ready for discharge); OR

Objectives	Endpoints
	
 Survival without need for mechanical ventilation or oxygen supplementation for the last 24 hours
Secondary Objectives	Endpoints for secondary objectives

 To demonstrate superiority of hydroxychloroquine or hydroxychloroquine plus azithromycin compared to placebo in achieving viral clearance by Day 15 	
 The percentage of participants with negative or below the lower limit of quantification LLOQ SARS-COV-2 based on polymerase chain reaction (PCR) test by Day 10

 To evaluate the time to discharge from the hospital in participants receiving hydroxychloroquine or hydroxychloroquine plus azithromycin relative to placebo 	
 Time to discharge (or ready for discharge)

 To evaluate the time to return to pre-morbid supplemental oxygen requirement in participants receiving hydroxychloroquine or hydroxychloroquine plus azithromycin relative to placebo 	
For the subset of patients who require supplemental oxygen at the time of randomization:
 
 Time to return to pre-morbid supplemental oxygen requirement

 To evaluate the time to SARS-CoV-2 negativity in participants receiving hydroxychloroquine or hydroxychloroquine plus azithromycin relative to placebo 	
 Time to SARS-CoV-2 negativity

 To assess safety of participants receiving hydroxychloroquine or hydroxychloroquine plus azithromycin as compared to placebo 	
 Number of participants with adverse events (AE), serious adverse events (SAE), clinically significant changes in laboratory measures, ECG and vital signs

[REDACTED]
	
[REDACTED]

[REDACTED]	[REDACTED]

2 Statistical methods

2.1 Data analysis general information

Novartis statistical and programming team will perform the CSR analysis as planned in this document.

Statistical Analysis System (SAS) software version 9.4 will be used to perform statistical analysis.

Unless otherwise specified, descriptive summaries for categorical data will include frequencies and percentages, and continuous data will be presented with mean, standard deviation, median,

minimum, and maximum. For selected parameters, 25th and 75th percentiles may also be presented.

2.1.1 General definitions

2.1.1.1 Terminology – Study drug

In this document the following terminology is used

- **Study drug or study medication or study treatment** always refers to randomized double-blind study drug
- **Standard of care:** It is considered that all participants will receive best standard of care as background therapy.

2.1.1.2 Study days

Study day 1 and Date of first administration of study drug/treatment

Study Day 1 (or Day 1 or reference start date) is defined as the first day of administration of randomized study medication (i.e. the date of first dose of the study drug). For participants with missing first dose date (for example mis-randomized participants), study day 1 will be defined based on the randomization date.

All other study days will be labeled relative to Day 1.

For events with dates on or after Day 1, study day for the event is calculated as (event date – first dose date + 1). For events with dates before Day 1, study day for the event is calculated as (event date – first dose date).

Duration of an event is calculated as (event end date – event start date +1).

Day post-study drug discontinuation

Day post-study drug discontinuation for a particular event is calculated as (event date – study drug discontinuation date). The date of study drug discontinuation will be the date of the last dose of study drug.

Day post-study drug discontinuation will be included in listings to facilitate identification of events/data occurring/collected post study drug discontinuation and to provide information on how long after study drug discontinuation the event/data occurred/was collected. Day 0 and negative days will not be used.

2.1.1.3 Baseline

The derived baseline is defined as the last assessment obtained prior to start of treatment (i.e. prior to study Day 1). In the situation where the screening visit was conducted on study day 1, the derived baseline will be defined as the assessment performed at the screening visit.

For ECG parameters

Baseline is defined as the Day 1 pre-dose value. If unavailable, the assessment made at last visit (screening visit or unplanned) before first dose date will be used. A screening visit

conducted on study day 1 will be considered to have been performed prior to first dose administration.

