8.2 Participant demographics/other baseline characteristics

All baseline assessments must be performed prior to first study treatment administration. These may be in the screening period (e.g. demographics) or at the randomization visit, depending on the assessment.

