12.4.2 Statistical model, hypothesis, and method of analysis

The numbers and percentages of responders will be summarized by treatment group. The difference in observed response rates between active treatment groups and placebo arms will be presented along with 95% confidence intervals. The statistical hypothesis tested for clinical response is that there is no difference in the proportion of participants achieving clinical response at Day 15 with hydroxychloroquine or hydroxychloroquine plus azithromycin plus versus placebo.

Let p_j denote the proportion of clinical responders at Day 15 for treatment groups j , $j = 0, 1, 2$ where

- 0 corresponds to placebo
- 1 corresponds to hydroxychloroquine plus azithromycin
- 2 corresponds to hydroxychloroquine

The following statistical hypotheses will be tested to address the primary efficacy objective:

$$H_1: \frac{P_1(1-P_0)}{P_0(1-P_1)} = 1, H_{A1}: \frac{P_1(1-P_0)}{P_0(1-P_1)} \neq 1$$

$$H_2: \frac{P_2(1-P_0)}{P_0(1-P_2)} = 1, H_{A2}: \frac{P_2(1-P_0)}{P_0(1-P_2)} \neq 1$$

In other words,

H_1 : hydroxychloroquine plus azithromycin is not different to placebo with respect to the likelihood of clinical response by Day 15

H₂: hydroxychloroquine is not different to placebo with respect to the likelihood of clinical response by Day 15

The primary efficacy endpoint of clinical response at Day 15 in the FAS will be evaluated using a logistic regression model with treatment group and whether or not supplemental oxygen is required at randomization as explanatory variables. Odds ratios will be computed for each of active treatment comparisons to placebo. Based on what data is available from the evolving COVID-19 literature, it is anticipated that hydroxychloroquine plus azithromycin will have a greater clinical response than hydroxychloroquine and thus each of the primary and secondary hypotheses will be tested first in a closed testing procedure in order to preserve familywise Type I error rate at 0.05 two-sided. Details of the closed testing procedure are provided in [Section 12.5](#).

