2.1.1.7.1 Rule for re-mapping visits which are not time-point specific

The early discharge visit and unplanned assessments, which are not time point specific, will be remapped to one of the scheduled time-point based on rules provided in [Table 2-1](#), [Table 2-2](#) and [Table 2-3](#). The remapped visit will only be used in analysis, in case the corresponding schedule visit is missing.

Table 2-1 Remapping rule for vital signs

Visit	Visit window (study days)	Target Day
Baseline*	See Section 2.1.1.3	
Day 1	1	1
Day 2	2, 3	2
Day 4	4, 5	4
Day 6	6, 7	6
Day 8	8, 9	8
Day 10	10,11	10
Day 40	12 to 40	40

* Note: A screening assessment performed on study day 1, will be mapped to the baseline visit.

Table 2-2 Remapping rule for Lab (Hemathology, Chemistry, Inflammatory markers)

Visit	Visit window (study days)	Target Day
Baseline*	See Section 2.1.1.3	
Day 1	1	1
Day 4	2 to 6	4
Day 10	7 to 12	10
Day 15	13 to 17	15
Day 40	18 to 40	40

* Note: A screening assessment performed on study day 1, will be mapped to the baseline visit.

Table 2-3 Remapping rule for ECG

Visit	Visit window (study days)	Target Day
Baseline*	See Section 2.1.1.3	
Day 1§	1	1
Day 2	2, 3	2
Day 4	4, 5	4
Day 6	6, 7	6
Day 10	8 to 12	10
Day 40	13 to 40	40

* Note: A screening assessment performed on study day 1, will be mapped to the baseline visit.

§ only applies to unplanned assessment performed on Day 1. For assessment performed at “Day 1-pre-dose” or at “Day 1 4 hours post-dose”, remapped visit (AVISIT) will be labelled “Day 1 pre-dose” or “Day 1 4 hours post-dose”.

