2.3.2 Background and demographic characteristics

Participant demographic and baseline characteristics will include:

- Age
- Age categories (≤ 65 , > 65 years)
- Sex
- Race
- Ethnicity
- Height
- Weight

[figure not shown]
- BMI

Background disease characteristics will include:

- Oxygen saturation at baseline ($\leq 94\%$; $> 94\%$)
- Requiring supplemental oxygen at baseline (No/Yes)
- Supplemental Oxygen Flow rate (L/min) (see also [section 2.4.2.3](#))
- Number of days from onset of symptoms to first dose of study drug
- Number days from hospital admission to first dose of study drug
- Chest imaging (x-ray or CT scan) status at baseline (Normal/Abnormal/not available)
- Pre-morbid oxygen requirement (No/Yes)
- 
- Tachypnea (i.e. respiratory rate > 24 bpm) at baseline (No/Yes)

Comorbidities will include:

- Number of comorbidities (0,1 >1) , where comorbidities include the following list of solicited terms: Cerebrovascular disease, Chronic heart disease, Hypertension, Asthma, COPD, Chronic kidney disease, Malignant neoplasm, Diabetes.

Demographic and other baseline data will be summarized descriptively by treatment group for all study participants in the FAS.

Categorical data will be presented as frequencies and percentages. For continuous data, mean, standard deviation, median, minimum, and maximum will be presented. For selected parameters, 25th and 75th percentiles will also be presented.

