2.4.2.3 Supplemental oxygen therapy

Supplemental oxygen therapy was solicited at the Screening, Day 1, Day 2, Day 4, Day 6, Day 8, Early Discharge/Day 10, at follow-up Day 15 visit and at EOS/Day 40. This assessment included a measure of Oxygen Flow rate in L/min.

Oxygen flow rate (L/min) at baseline will be analyzed using descriptive summary statistics. For patient who did not receive supplemental oxygen therapy at baseline, Oxygen Flow rate (L/m) will derived as 0. This parameter will be reported along with other background disease characteristics (see [section 2.3.2](#)).

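### SAP 2.1.1.3 keeps Day 1 visit values out of the non-ECG baseline, so participants screened earlier get vital-sign and oxygen baselines that are 1 to 4 days old

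*SAP*

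**What the plan says.** - SAP 2.1.1.3 defines the general baseline as the "last assessment obtained prior to start of treatment (i.e. prior to study Day 1". SAP 2.1.1.2 makes Day 1 a calendar date, "defined as the first day of administration of randomized study medication".
- There is one exception: when screening itself takes place on Day 1, its reading serves as baseline. The notes under Tables 2-1 to 2-3 repeat it: "A screening assessment performed on study day 1, will be mapped to the baseline visit".
- ECG has its own rule in SAP 2.1.1.3. Its baseline is the Day 1 pre-dose value, with an earlier visit as fallback.
- Protocol 8.2 requires baseline assessments to precede first dosing and adds: "These may be in the screening period (e.g. demographics) or at the randomization visit, depending on the assessment".
- Protocol 12.2 lists oxygen requirement at randomization as a baseline characteristic, and the model in Protocol 12.4.2 adjusts for "whether or not supplemental oxygen is required at randomization". SAP 2.3.2 instead tabulates "Requiring supplemental oxygen at baseline (No/Yes").
- Oxygen data exist at both times: "Supplemental oxygen therapy was solicited at the Screening, Day 1, Day 2" and later visits (SAP 2.4.2.3). Protocol Table 8-1 schedules vital signs at both Screening and Day 1.
- SAP Section 4 declares no change to the protocol's analyses.

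**The concern.** The SAP treats two conditions as one when they differ. Before start of treatment is a matter of clock time; before Day 1 is a matter of date. Readings taken on Day 1 before the first dose fall in the gap.

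In hospitalized patients with COVID-19, oxygen need and vital signs can move within days. A table meant to describe participants when they were randomized could then describe them up to four days earlier. ECG and vital-sign baselines could come from different days in the same participant. A Day 1 vital sign taken before dosing would also be reported as change from baseline under treatment, although SAP 2.8 confines the safety analysis to data collected once treatment has begun.

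**Working it through.** The plan states no figure to reproduce here. The check is textual, with some date arithmetic.

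**1. The two conditions.** Let the first dose be given at time t0 on date D1. Condition A is assessment time < t0. Condition B is assessment date < D1. B implies A, but A does not imply B. The difference is exactly the set of readings on D1 taken before t0.

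**2. Which condition operates.** The parenthesis glosses A as B. Two further features fit B:
- The Day 1 screening exception would be largely unnecessary if Day 1 pre-dose values already counted.
- Table 2-1 has separate Baseline and Day 1 rows, and its note moves only a screening assessment from Day 1 to Baseline.

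A programmer following the text would use the screening value for anyone screened before Day 1.

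**3. Age of that value.** Protocol Table 8-1 puts screening on days -3 to 0, with first dose on Day 1. For screening on protocol day d, the age in calendar days is 1 - d:
- d = -3: 4 days
- d = -2: 3 days
- d = -1: 2 days
- d = 0: 1 day

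If screening is on Day 1, the age is 0 and the exception applies. An unscheduled reading between screening and Day 1 would shorten the gap.

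**4. Which variables have a Day 1 value to lose.**
- Affected: vital signs collected on Day 1 (including SpO2 and respiratory rate), supplemental oxygen requirement and oxygen flow rate.
- Not affected: laboratory tests, which have no scheduled Day 1 sample (Protocol Table 8-1, SAP 2.8.3); height and weight, which are collected at screening only; and ECG, which has its own rule.

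**5. Where derived baseline is used.**
- Used: the SpO2 category, oxygen requirement, oxygen flow rate and tachypnea rows of SAP 2.3.2, and the vital-sign change-from-baseline summaries of SAP 2.8.4.2.
- Not used: the primary endpoint, which depends on pre-morbid oxygen requirement (SAP 2.5.1), and the oxygen summary in SAP 2.7.1, which runs on the FAS and is defined by pre-morbid requirement and current support. SAP 5.4 states that no statistical model is implemented.

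**6. How many.** SAP 1.1 gives 20 randomized, one of them mis-randomized. The number screened before Day 1 is not given, so the range is 0 to 20 randomized. At most 20 - 1 = 19 of them can enter the FAS and safety-set tables. Assuming an even split, 19 / 3 = 6.3, so arms of 6 or 7. One participant in the wrong baseline category then moves that arm's percentage by 1/7 = 14 to 1/6 = 17 points. How often oxygen status changed between screening and Day 1 is also not given, so the number misclassified cannot be computed.

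**The case against.** The best defence is timing. Only the ECG has a stated Day 1 pre-dose time (Protocol Table 8-1 and 8.4.4). No document says whether Day 1 vital signs or oxygen status are recorded before or after the first dose. Protocol 8.2 does not settle it: it permits baseline at the randomization visit without saying that Day 1 vital signs are baseline assessments. The preferred order in Protocol 8.4.4, ECG first and vital signs next, makes a pre-dose reading plausible, but Day 1 also has an ECG four hours after dosing. Protocol 6.5.1 puts dosing times in source documents, which does not guarantee that they, or vital-sign times, reach the database. On this view, using Day 1 only where a pre-dose label exists keeps post-dose values out of baseline.

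Much of this stands. That Day 1 vital signs are pre-dose is an inference, and any fix needs a rule for untimed values. But the SAP's rule does not turn on timing. It excludes a Day 1 reading even when it is known to be pre-dose, and it does so while its own main clause would admit that reading. Nor does the defence explain why oxygen requirement is reported at derived baseline when the protocol lists it as of randomization and SAP Section 4 records no change.

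A reader might go further and infer that the rule misclassifies an oxygen stratum, the model covariate, or the subset for the time-to-oxygen endpoint. The documents do not support that for the planned report. Protocol 6.3.2 describes no stratification by oxygen. The logistic model and the oxygen subgroup analysis belong to the protocol and are not carried into this abbreviated SAP. SAP Table 1-1 defines the oxygen subset at randomization, but SAP 2.7.1 analyzes the FAS.

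**Conclusion.** The point holds for vital signs and supplemental oxygen in participants screened before Day 1. Their baseline comes from a value 1 to 4 days old, although a Day 1 value is scheduled. For oxygen this departs from Protocol 12.2; for the rest it passes over an option that Protocol 8.2 allows and that the SAP already uses for ECG. Separately, and only if Day 1 vital signs were taken before dosing, the Day 1 change-from-baseline row conflicts with SAP 2.8.

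It would be too broad to say that every non-ECG baseline is affected: laboratory tests, height, weight and anyone screened on Day 1 are not.

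The size is small and cannot be fixed more closely than 0 to 20 randomized participants. No efficacy result in the SAP changes; the affected output is descriptive. With arms of about 6 or 7, though, a single outdated oxygen status is visible in a percentage, so the correction is worth making.

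**What to change.** - Define non-ECG baseline as the last non-missing assessment before the first dose, including Day 1 values timed or labelled pre-dose. The Day 1 screening exception can stay.
- State a convention for untimed Day 1 values. For example, treat the Day 1 visit value as pre-dose unless its recorded time is after the first dose, and flag it in listings.
- Report oxygen requirement and flow rate at randomization (Day 1), with the screening value as fallback.
- Do not present a pre-dose Day 1 vital-sign value as a post-baseline visit.

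The cost is about one sentence in SAP 2.1.1.3, the accompanying convention and a programming change, with no new visits or assessments. If assessment times are not in the database, the convention does most of the work. The downside is small: an untimed Day 1 value may occasionally be post-dose, and the flag makes such cases visible.

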2.1.1.4 Date of Last contact

For participant who dies, the date of last contact will be the date of death. For other participants the date of last contact will be derived as the last visit assessment date.

2.1.1.5 Analysis cut-off

Unless otherwise specified all data should be used in analysis.

2.1.1.6 Treatment-emergent data

Treatment-emergent data will be defined as data collected after the start of the study treatment until respective cut-off dates

2.1.1.7 By-visit summary

By-visit summary will be provided for the following safety endpoints: ECG, vital signs and Lab (Hemathology, Chemistry, Inflammatory markers). *Nominal visits* (i.e. the scheduled visits collected in the database) will be used to summarize these endpoints.

For efficacy endpoints: the score achieved on the 9-item ordinal scale by Day 15 or by Day 28 will be reported. Accordingly, nominal visits will not be used. For this analysis, in case more than one assessment were performed on the same day, schedule assessment will be preferentially used.

Viral clearance will be reported by Day 6 and by Day 10; nominal visits will not be used to summarize these endpoint.

2.1.1.7.1 Rule for re-mapping visits which are not time-point specific

The early discharge visit and unplanned assessments, which are not time point specific, will be remapped to one of the scheduled time-point based on rules provided in [Table 2-1](#), [Table 2-2](#) and [Table 2-3](#). The remapped visit will only be used in analysis, in case the corresponding schedule visit is missing.

Table 2-1 Remapping rule for vital signs

Visit	Visit window (study days)	Target Day
Baseline*	See Section 2.1.1.3	
Day 1	1	1
Day 2	2, 3	2
Day 4	4, 5	4
Day 6	6, 7	6
Day 8	8, 9	8
Day 10	10,11	10
Day 40	12 to 40	40

* Note: A screening assessment performed on study day 1, will be mapped to the baseline visit.

Table 2-2 Remapping rule for Lab (Hemathology, Chemistry, Inflammatory markers)

Visit	Visit window (study days)	Target Day
Baseline*	See Section 2.1.1.3	
Day 1	1	1
Day 4	2 to 6	4
Day 10	7 to 12	10
Day 15	13 to 17	15
Day 40	18 to 40	40

* Note: A screening assessment performed on study day 1, will be mapped to the baseline visit.

Table 2-3 Remapping rule for ECG

Visit	Visit window (study days)	Target Day
Baseline*	See Section 2.1.1.3	
Day 1§	1	1
Day 2	2, 3	2
Day 4	4, 5	4
Day 6	6, 7	6
Day 10	8 to 12	10
Day 40	13 to 40	40

* Note: A screening assessment performed on study day 1, will be mapped to the baseline visit.

§ only applies to unplanned assessment performed on Day 1. For assessment performed at “Day 1-pre-dose” or at “Day 1 4 hours post-dose”, remapped visit (AVISIT) will be labelled “Day 1 pre-dose” or “Day 1 4 hours post-dose”.

2.1.1.7.2 Handling of multiple assessments within visit windows

In case multiple assessments of a participant may fall in a particular window, all results will be displayed in listings, but for summary statistics, only the value closest to the actual target day will be used. If two assessments are separated by the same number of days from the target day, the earlier assessment will be used. If an unplanned or unscheduled assessment (e.g. discharge visit) were conducted on the target day but a schedule assessment for this assessment is also available, the schedule assessment will be used.

2.1.1.8 Participants

Every effort should be made to use the term participant instead of the term patient or subject in this SAP and in the CSR deliverable of the JWT629A12301 trial.

2.1.1.9 Missing and partial dates

The general approach to handling missing dates is described in [Section 5.1](#).

2.2 Analysis sets

The **Randomized Analysis Set (RAS)** consists of all randomized participants regardless of receiving study treatment.

The **Full Analysis Set (FAS)** comprises all participant to whom study treatment has been assigned by randomization excluding mis-randomized participants. Mis-randomized participants are defined as cases where IRT contact is made by the Investigator/qualified site staff either prematurely or inappropriately prior to confirmation of the participant's final randomization eligibility and treatment is not administered to the participant. According to the intent to treat principle, participants will be analyzed according to the treatment they have been assigned to during the randomization procedure.

The **Safety Set (SAF)** includes all participants who received at least one dose of study treatment. Participants will be analyzed according to the study treatment received, where treatment received is defined as the randomized/assigned treatment if the participant took at least one dose of that treatment or the first treatment received if the randomized/assigned treatment was never received.

The analysis of the primary objective and all other efficacy variables will be performed on the FAS. The Safety Set will be used in the analysis of all safety variables.

